5.5 Supportive Care, Other Concomitant Therapy, Prohibited Medications

The Research Nurse and CRAs will review participant's responses to all self-reported outcome measures and alert the attending thoracic surgeon if participants show risk of self-harm or other serious conditions. These participants will be referred to supportive care and social work as necessary after evaluation by the attending surgeon. Otherwise, there are no restrictions to the use of supportive care medications, other concomitant therapy and no prohibited medications.

5.6 Additional Studies

Patients enrolled in the study will be consented to provide permission to access their routine CT scans for future research purposes. The future use involves improving the knowledge on accurate methods of measuring muscle mass. The study will access routine CT scans before surgery and scans at 6-months after surgery. Patients will not incur additional costs or harms because only routine CT scans completed for treatment preparation and for follow-up will be used.

All outcome measures, as described below, are available and validated in both English and Chinese.

FCGs and patients will also complete Geriatric Assessments (GA), available in both English and Chinese. All participants, regardless of age, will complete GA throughout the study. In our previous Program Project grant in lung cancer, we had completed GA for all patients, regardless of age. Many key components of the GA (such as comorbidities, social support, social activity, weight loss, body mass index) are relevant outcomes to consider for all surgical patients, regardless of age. In addition, we anticipate that many FCGs will be older. Our administration of the GA in FCGs is exploratory, and will provide an innovative approach to expand the utility of GA in oncology.

The Geriatric Assessment (GA) Tool developed by Hurria and colleagues is composed of a group of instruments, some of which are completed by the research staff and some by the patient. Each of these is described below. Time for patients to complete the group of questionnaires is 27 minutes.^{88, 89}

- 1) Instrumental Activities of Daily Living (IADL): [subscale of the Older American Resources and Services (OARS)] The OARS Multidimensional Functional Assessment Questionnaire (MFAQ) was developed to provide a profile of the level of functioning and need for services of older persons who live at home but may have some degree of impairment. The MFAQ has been tested on over 6,000 older community residents. ⁹⁰ The Instrumental Activities of Daily Living (IADL) subscale consists of 7 questions rated on a three-point Likert scale of degree to which the activity can be performed independently. Norms are available for the MFAQ based on 2,146 elderly community residents. ⁹⁰
- 2) Activities of Daily Living: [subscale of Medical Outcomes Study (MOS) Physical Health] The MOS Physical Health Scale contains measures of higher levels of physical functioning than

IRB 17238 02/02/2023

[figure not shown]
those described in other activities of daily living scales. The variation in functioning among healthier patients in the study will be examined through asking about higher order functioning. The scale includes items on vigorous activities (running, lifting heavy items) as well as basic activities (bathing and dressing). The 10 items are rated on a three-point Likert scale of independent performance of the activity. At least six items must be answered to obtain a total score. A total score is created by summing the item scores and transforming them to range from 0 to 100. Internal consistency of the physical function score is high at 0.92.91

- 3) Karnofsky Physician-Rated Performance Rating Scale (KPS): The Karnofsky Performance Status, has been widely used in the evaluation of cancer patients. 92 It is a general measure of patient independence in carrying out normal activities. Patients are given a score on a numerical scale of 0-100 as a global indicator of functional status. Studies on inter-rater reliability between nurse and social worker KPS ratings indicate good correlation (r = 0.69, p < .001). KPS was most strongly correlated with variables related to physical functioning (difficulty with stairs: r = 0.63; difficulty with balance: r = 0.61).
- 4) Timed Up & Go: The timed "up and go" is a test of physical mobility. The test, measured in seconds, is the time it takes for an individual to stand up from a standard arm-chair (approximate seat height of 46 cm), walk a distance of 3 meters (10 feet), turn, walk back to the chair, and sit down again. Intra-rater and inter-rater reliability was extremely high (intra-class correlation 0.99). Performance on the timed "up and go" test significantly correlated with scores of other performance measures including Berg Balance Scale (r = -0.81), gait speed (r = -0.61), and Barthel Index of ADL (r = -0.78).
- 5) Number of Falls in Last 6 Months: Older patients are at risk for falls and injury secondary to falls because of gait and balance impairments. In patients with cancer the risk is even greater for a number of reasons. First, bony metastases may place them at risk of a pathologic fracture with falls. Secondly, patients receiving chemotherapy may have a low platelet count which puts them at greater risk of hemorrhage. Lastly, commonly used chemotherapy drugs may have neurologic complications resulting in falls. For example, paclitaxel and cisplatin may cause neuropathy, fluorouracil and cytarabine may cause cerebellar toxicity. For these reasons, knowing a patient's risk of falling before treatment could help providers make treatment decisions.
- 6) Physical Health Section [subscale of The Older American Resources and Services Questionnaire (OARS)]: The OARS Physical Health Section is a comorbidity scale which contains a list of concurrent illnesses and the degree to which they impair daily activities, rated on a three-point scale of "not at all" to "a great deal." Medication use is recorded. Test-retest reliability was good (r=.66) over a five-week period. In terms of validity, the Physical Health subscale correlated significantly with health professional ratings (Kendall's tau co-efficient =.75). We will also capture the patient's medication list, so as to confirm that the comorbidity list reported by the patient is complete.
- 7) Blessed Orientation-Memory-Concentration Test: The BOMC consists of 6 questions designed to screen for gross cognitive impairment. A score >11 signifies cognitive impairment. The test-retest reliability is high (Spearman Rank Correlation 0.96; p < 0.001). The BOMC has excellent validity as a screening instrument, correlates highly with clinicians' ratings of dementia severity (r=0.89), predicts results from a longer (26 item) mental status questionnaire, and discriminates between patients with mild, moderate, and severe cognitive deficits.
- 8) Hospital Anxiety and Depression Scale (HADS): The Hospital Anxiety and Depression Scale (HADS) is a 14-item self-administered measure that has been well tested in cancer populations. It has two 7-item subscales that assess depression and anxiety. The scale is considered

IRB 17238 02/02/2023

particularly appropriate for use with medically ill patients because of the absence of somatic items that often confound the determination of psychiatric problems in a medically ill population. Reported anxiety and depression cutoff scores on the HADS have varied from 8 to 11. The total cutoff score for psychological distress has ranged from 13, reflecting adjustment disorder, to 19, reflecting major depressive disorders. Ibbotson and colleagues found that an overall cutoff score of 15 or greater resulted in 80% sensitivity, 76% specificity, and a positive predictive value of 41% for psychological distress.⁹⁴

- 9) Medical Outcomes Study (MOS) Social Activity Limitations Measure: The impact of cancer on patients' social functioning will be assessed by the Social Activity Limitations scale from the Medical Outcome Study (MOS). As with all MOS measures, the Social Activity Limitations scale was developed from a national sample of medically ill patients being treated in outpatient facilities. The four-item scale assesses the extent to which physical or emotional problems have interfered with social activities. All items are rated on a 5-point Likert scale, with response categories varying with each item. The mean of the total score is transformed to a scale of 0-100, with a higher number indicating greater support. Internal consistency was good (alpha coefficient = .77). The scale correlates significantly with a range of measures: role limitations due to physical (r=.52) and emotional (r=.49) health, psychological distress (r=.64) and pain (r=.55).
- 10) Medical Outcomes Study (MOS) Social Support Survey: Emotional/Information and Tangible Subscales: This is a 20-item measure of social support, with four subscales: emotional/informational, tangible, affectionate, and positive social interactions. The scale was developed as part of the Medical Outcome Study, tested on 2987 patients, and designed to assess quality of life across medical conditions. In this study, we use the Tangible (access to material aid or behavioral assistance) and Emotional/Information (the expression of positive affect and empathetic understanding; the offering of advice, information, guidance, or feedback) subscales. All but one item is rated on a five-point Likert scale from "None of the Time" to "All of the Time." Internal consistency of the subscales and total score are excellent (alpha coefficient > 0.91). Convergent validity was demonstrated by significant correlations of social support total score with measures of mental health (r = .45). 91
- 11) Percent Unintentional Weight Loss: Patients will be asked to quantify the amount of unintentional weight loss in the past 6 months and to record their baseline body weight 6 months ago. The following is the calculation for % unintentional weight loss: unintentional weight lost in last six months = (unintentional weight loss in last 6 months/baseline body weight) x100.
- 12) Body Mass Index: Weight and height will be measured in order to calculate body mass index, by the following formula:

The assessments will be completed in-person on an iPad during a routine clinic visit, or by telephone. Patients will complete GA at baseline, first postoperative clinic visit, and 3 months. FCGs will complete GA at baseline and 3 months).

13) Mini-Cog: The mini-cog is a validated tool recommended for use to assess Chinese speaking participants in place of the blessed-orientation-memory-concentration test. A score of <3 is a validated cut off for dementia screening, although a score of <4 may be used for more sensitive screening of cognitive impairment.

IRB 17238 02/02/2023

COVID-19 Questions- These questions will be asked 1 month post-discharge to obtain qualitative data from patients and FCGs on the impact of the COVID-19 pandemic. FCGs and patients will provide answers separately. We will only collect this data going forth with newly enrolled patients/FCGs. We will not ask patients/FCGs already enrolled in the study to complete the questions.

COVID-19 Interview Questions for Healthcare Professionals – These interview questions will be used to obtain qualitative data from thoracic surgeons and thoracic surgery nurse practitioners on the impact of COVID-19 on cancer care. Interviews will be conducted individually with each surgeon/NP (total = 5). Interviews will be conducted once only.

Social Determinants of Health (SDH) – Key Informant Interviews: Six participants (3 FCGs, 3 patients) will be invited to participate in individual (Key Informant) interviews. The purpose of the 6 interviews is to inform the development of the interview guide to determine social determinants of health-related needs of FCGs/patients in relation to lung cancer surgery. A total of 30 participants (15 FCGs, 15 patients) will then be invited to participate in individual (Key Informant) interviews. A total of 36 FCGs/patients (3 FCG/patient dyads) will be randomly invited to participate in six focus groups. Open-ended questions will be used to garner discussions around SDH and QOL outcomes for FCGs and patients.

Invitation letters will be sent to potential participants via email and postal mail; the letters will instruct interested participants to contact the investigators ([name]). Each key informant interview will last approximately 30 minutes and each focus group session will last approximately 60 minutes. Both will be conducted via Zoom or MS Teams videoconferencing to minimize travel burden for participants. Set-up for the Zoom/MS Teams system and instructions for use will be provided prior to each interview. Only newly enrolled dyads after IRB approval will be invited to participate in the interviews. Dyads that are already enrolled will not be invited.

Social Determinants of Health (SDH) – Quantitative Survey: FCGs and patients will complete the following questionnaire about the impact of social determinants of health. For English-speaking participants who enrolled in the study but did not complete the SDH quantitative survey, they will be retrospectively invited to complete the survey at one time only. Participants will be consented using IRB approved addendum consents before survey completion.

Protocol for Responding to and Assessing Patients' Assets, Risks, and Experiences (PRAPARE)⁹⁵: This 21-item instrument measures SDH domains for patients related to environment, economic stability and social and emotional health factors. PRAPARE is a standardized patient and social risk assessment tool informed by research on SDH and aligns with national initiatives (e.g. Department of Health and Human Services' Healthy People 2020), federal reporting requirements, and International Classification of Diseases-10 clinical coding system.

Spiritual Well-Being — Quantitative Survey: _Patients will complete the following questionnaire about spiritual well-being. For English-speaking participants who enrolled in the study but did not complete the Spiritual Well-Being quantitative survey, they will be retrospectively invited to complete the survey at one time only. Participants will be consented using IRB approved addendum consents before survey completion.

IRB 17238 02/02/2023

Functional Assessment of Chronic Illness Therapy-Spiritual Well-Being Scale (FACIT-Sp-12): This 12-item tool assesses a patient's spiritual well-being using a 5-point Likert scale. FACIT-Sp-12 measures sense of meaning and peace (8-item subscale), and the role of faith in illness (4-item subscale). The internal consistency ranges from 0.81 to 0.88 for the total scale and subscales. Items score ranges from 0 to 48 and a higher score indicates better spiritual well-being. The tool was previously tested in a sample of lung cancer patients. FCGs will not complete the survey.

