We will use semi-structured interviews to examine dyadic experiences with the MSM Intervention. Qualitative data will be analyzed by the PIs using the conventional content analysis approach. This approach is used to describe a phenomenon where existing theory or research literature is limited. Data from the tape-recorded interviews will be transcribed and analyzed using HyperRESEARCHTM qualitative software. Transcripts will be imported allowing for the development of analytic categories, data coding, and review of coded data. All data will be read repeatedly to achieve immersion and obtain a sense of the whole. Then, data will be read word by word to derive codes. Codes will then be sorted into themes based on links and relationships. Separate investigators with experience in qualitative data analysis ([name] and [name]) will conduct a final validation review of the codes and themes to ensure consistency and clarity across all qualitative data. Data discordantly coded will be discussed for refinement and consensus purposes.

Geriatric Assessment (GA) data for both FCGs and patients will be analyzed descriptively. We will use descriptive statistics (mean [SD], median [range], percentage [95% confidence interval]) to summarize GA scores and domains. We will also describe the patterns of changes in GA over time for both FCGs and patients. Changes will be calculated as post-surgery scores minus pre-surgery scores. Exploratory logistic regression models (univariate and multivariate) will be fitted to study the correlation between GA and FCG/patient outcomes.

COVID-19 qualitative data will be analyzed using content analysis approaches as described under exploratory aim 2.

Social determinants of health (SDH) data will be scored according to guidelines descriptively summarized. We will use multiple linear regression to test associations between baseline outcomes and SDH predictors. Baseline scores of outcomes activation, burden preparedness, self-efficacy, QOL and distress will be summarized with descriptive statistics. Distributions of SDH predictors will be summarized. For each outcome, we will use bivariate regression to assess the effect of one predictor at a time. Stepwise multivariate analysis will be performed to select all significant predictors (p<0.05). In addition, multicollinearity issues will be examined by calculating correlation matrix for all predictors and by checking variance inflation factors.

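### Falls and unintentional weight loss keep a 6-month recall at follow-up, so the planned post-minus-pre change is attenuated for falls and can hide or reverse a post-operative weight loss

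*Combined protocol and SAP*

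**What the plan says.** Section 5.6 lists the components of the geriatric assessment (GA). Item 5 is headed "Number of Falls in Last 6 Months". Item 11 reads "Patients will be asked to quantify the amount of unintentional weight loss in the past 6 months" and asks patients "to record their baseline body weight 6 months ago", which is the denominator of the percentage. Item 12 adds that "Weight and height will be measured in order to calculate body mass index".

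On timing, the same section says "Patients will complete GA at baseline, first postoperative clinic visit, and 3 months", and "FCGs will complete GA at baseline and 3 months". The study calendar in section 10 agrees. Neither place gives a shorter recall period for the follow-up assessments. Section 5.2 puts total participation at about 3 to 4 months.

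On analysis, the GA paragraph near the end of section 13.1 says "Geriatric Assessment (GA) data for both FCGs and patients will be analyzed descriptively", and then "Changes will be calculated as post-surgery scores minus pre-surgery scores". It makes no exception for items that carry their own look-back period. It also plans exploratory logistic regressions relating GA to caregiver and patient outcomes.

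**The concern.** Most GA components describe the participant's state at the time of assessment, so subtracting the pre-surgery value from the post-surgery value makes sense. These two items describe a period. When the period is 6 months and the last assessment comes about 3 months after discharge, the value labelled post-surgery covers pre-surgery time, and part of it is the same time that the baseline value covers.

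What is at stake is the pre/post description itself, which is the planned GA result. Section 5.6 names weight loss among the GA components relevant to all surgical patients, and section 13.1 plans to describe how GA changes over time. A reader of those tables would take a small or negative change to mean that falls or weight loss did not worsen after surgery. For these two items that reading could be wrong.

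**Working it through.** The plan states no sample size, power or error rate for these items, so there is no figure to reproduce. The check is arithmetic on the recall windows.

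**Inputs from the documents.** Recall W = 6 months (182.5 days). Last GA at 3 months post-discharge (91 days). Baseline is completed after consent (section 4.3), with no stated interval to surgery.

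**Assumptions.** Baseline 3 to 30 days before surgery (worked case 7), hospital stay 3 to 10 days (worked case 5), first postoperative visit 7 to 28 days after discharge (worked case 14). All fall rates and weights below are illustrative.

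**Window content.** Share before surgery = (W - days since surgery)/W. Share repeating the baseline window = (W - days since baseline)/W.

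| Assessment | Before surgery | Repeats baseline window |
|---|---|---|
| First postoperative visit | 79-95% | 63-93% |
| 3 months post-discharge | 45-49% | 28-47% |

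For example, with a 3-day stay the 3-month window is (182.5 - 94)/182.5 = 48.5% pre-surgery.

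**Falls.** Falls in the shared segment enter both counts and cancel. The change equals falls since baseline minus falls in the oldest, equally long part of the baseline window. With rates r0 before and r1 after surgery (per 6 months), its expectation is:

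(post-surgery days x r1 + baseline-to-surgery days x r0 - days since baseline x r0)/W = (post-surgery days/W) x (r1 - r0)

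- First visit: 5 + 14 = 19 post-surgery days; 19/182.5 = 10.4% of the full-window change.
- 3 months: 5 + 91 = 96 post-surgery days; 96/182.5 = 52.6%.
- Over the assumed ranges: 10 to 38 days (5% to 21%) at the first visit, and 94 to 101 days (52% to 55%) at 3 months.

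A Poisson simulation (4,000 replicates, 160 patients as the retention target in section 13.1, r0 = 0.2) shows what this means in practice. The mean change differed from zero at the two-sided 5% level in 64% of runs at 3 months and 14% at the first visit when the rate doubled, and in 98.7% and 39% when it tripled.

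**Weight loss.** Take 80 kg six months before baseline, pre-baseline loss linear over those six months, and post-operative loss linear from surgery (day 7) to the 3-month GA (day 7 + 5 + 91 = 103). The 3-month reference date is then 182.5 - 103 = 79.5 days before baseline. With 6 kg lost before baseline, the reference weight is 80 - 6 x 103/182.5 = 76.61 kg.

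| Path | Baseline item | 3-month item | Planned change (points) | True loss since baseline |
|---|---|---|---|---|
| 6 kg before, none after | 6/80 = 7.50% | 2.61/76.61 = 3.41% | -4.09 | 0% |
| 6 kg before, 3 kg after | 7.50% | 5.61/76.61 = 7.33% | -0.17 | 3/74 = 4.05% |
| 3 kg before, 3 kg after | 3.75% | 5.50% | +1.75 | 3/77 = 3.90% |
| None before, 6 kg after | 0% | 7.50% | +7.50 | 7.50% |

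The first path looks like improvement although weight was stable. In the second, a real post-operative loss disappears.

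**The case against.** The best defence is that the change scores still carry information and that the plan asks little of them. Much of this stands.

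- A reader might infer that the change cannot show post-operative harm at all. It can. The overlap cancels for falls, so about half of a rate change survives at 3 months, and weight loss confined to the post-operative period is fully visible. Strong attenuation of falls applies mainly to the first visit.
- A reader might infer that pre-surgery falls are reported as post-surgery change. They inflate the displayed follow-up level, but a fall in the shared segment contributes zero to the difference. Nor is the pre-surgery share of the window the pre-surgery share of the count, unless the rate is constant.
- A reader might infer that the trial would wrongly clear surgery or the intervention of causing falls. No section gives these items a safety purpose. Section 5.6 justifies the falls item by risk before treatment, and section 13.1 plans no between-arm GA comparison. If arms were compared, randomization would balance pre-surgery experience on average, so the result would be diluted and noisier, not biased. Postoperative events, urgent care/ER visits and readmissions are recorded separately (section 12.1.3).
- The GA is an existing published tool, used in the team's earlier program project. Rewording it with participants already enrolled would break comparability and mix two recall definitions.

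What the defence does not answer is the subtraction rule. A pre-treatment purpose supports a 6-month recall at baseline. It does not support repeating that recall within about 3 months of discharge and presenting the difference as change after surgery.

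**Conclusion.** The concern holds in a limited form. The rule is stated, not merely left open, and for these two items it yields a misleading change score. For falls the change is attenuated, to about 10% of a full-window rate change at the first visit and about half at 3 months. For recalled weight loss it can hide or reverse a real loss when loss preceded baseline.

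The overlap follows from the documents. The percentages rest on assumed intervals from baseline to surgery and discharge to first visit, an assumed hospital stay, and constant fall rates before and after surgery. The weight figures are illustrations, not predictions.

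The reach is two components of a descriptive, exploratory assessment. No primary outcome, power figure or error rate changes.

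**What to change.** In the GA paragraph of section 13.1:

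1. Exempt falls and percent unintentional weight loss from the post-minus-pre rule.
2. Report each follow-up value with its look-back period, stating that it includes time before surgery.
3. Compute post-operative weight change from the weights measured for BMI at baseline and follow-up. Flag assessments done by telephone, which section 5.6 allows, where no weight was measured. Note that measured change does not separate intentional from unintentional loss.

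This is an analysis-text change, needs no new data, and also covers participants already assessed. Its cost is some missing weights and the loss of the intentional/unintentional distinction.

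Optionally, for participants not yet assessed, add a question on falls since surgery or since the last assessment (caregivers: since baseline) beside the existing item, and report falls per person-month. Keep the 6-month item for comparability with the published tool and earlier data. The added question has a shorter window than baseline, hence the need for rates, and will be missing for those already assessed.
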